4.1.1 Study Drug Administration Timing

In consideration of the latest time point of treatment application before graft reperfusion (ie. beginning of renal vein anastomosis), study treatments will be administered preoperatively at any one point in time, from time of admission up to the beginning of renal vein anastomosis **before graft** reperfusion. Due to the biologic half-life of C1INH (approximately 2.5 to 3.8 days), the time difference between early and late intraoperative treatment application, is thought to be negligible. In addition, the patients will receive study treatments at 24 hrs. post-transplant. This will constitute the entirety of C1INH vs. placebo administration. The study format is shown below in figure 3.

[figure not shown]

Figure 3: Study format to evaluate C1INH in DGF.

4.2 Selection Of Study Population

Persons legally incompetent to provide informed consent include, but may not be limited to, minors (children), individuals who are mentally incapable of understanding the implications of the PI/IC, and those who are physically unable, by any written, physical or verbal means, to confirm their understanding and consent to take part in the study. Our policy is not to enter adult patients who are mentally incompetent to give informed consent. Exceptions must be approved by the Study Director.

Up to 70 adult men and women (18-70 years of age) who are recipients of a kidney transplant and recipients of only a kidney allograft from a deceased donor who is high risk for DGF will be enrolled in the study.

CONFIDENTIAL

4.2.1 Inclusion Criteria

Recipient Inclusion Criteria

- 1). Adult men or women (18-70 years of age) who are on chronic dialysis therapy and acceptable candidates for kidney transplant.
- 2). Understand and sign a written informed consent prior to study specific procedures.
- 3). Recipients who are ABO compatible with donor allograft.
- 4). Recipients of kidney allograft from ECD* donors.
- 5). Recipients of kidney allograft from DCD** donors.
- 6). Recipients of kidney allograft other than ECD and DCD who have risk index of 3-8 (minimum 3 and maximum 8) for DGF, based on the criteria in the risk index detailed in Table 1.
- 7). Women of childbearing potential must have a negative pregnancy test prior to randomization, and must be on an acceptable form of birth control.

Table 1: Risk factors for Delayed Graft Function

Characteristic	Risk Index
Donor Age (years)	
<40	0
41-49	1
50-54	2
55-59	3
>60	6
Cold Ischemia time	
0-12	0
13-18	1
19-24	2
24-30	3
31-36	4
> 37	6
Recipient Race	
Non-Black	0
Black	1
Recipient with Diabetes	
Has Diabetes	1
No Diabetes	0
Donor cause of death due	
Donor age < 50 years	0
Donor age >50 years	3

*ECD Kidney: An ECD allograft is defined as a renal allograft donated for transplantation from a brain-dead donor over the age of 60 years or from a donor aged 50 to 60 years with two of the following: a history of hypertension, a pre-retrieval terminal serum creatinine greater than or equal to 1.5 mg/dl, or death from a cerebral vascular accident (stroke or aneurysm) (Cecka, 2004).

**DCD Kidney: Recovery of organs and or tissues from a donor whose heart has irreversibly stopped beating, previously referred to as non-heart-beating or asystolic donation (UNOS).

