Information regarding additional key personnel involved in the conduct of the study, including names and contact details of participating investigators, monitors, clinical laboratories, technical departments and/or institutions, as well as information on members of additional study committees, will be found in the study files of the sponsor and on site if requested.

A Data Safety Monitoring Board (DSMB) committee will review safety data. Quarterly assessment of AEs & SAEs will be performed and reported to CSL Behring, FDA and Cedars-Sinai IRB. In addition, DSMB must be informed and may be convened at any time questions about safety arise and/or thromboembolic events

occur. Please see appendix E for DSMB charter and FDA Guidance for Clinical Trial Sponsors.

4. Investigational PlanStudy Design And Plan

This is a Phase I/II double-blind, randomized, placebo-controlled study assessing safety and limited efficacy of intraoperative C1INH (50U/kg) vs. Placebo administered prior to graft reperfusion in adult subjects receiving a deceased donor kidney allograft considered high-risk for development of DGF. Patients will also receive an additional dose 24 hrs. post-transplant (C1INH (50U/kg vs. placebo). Once eligible patients are identified, consented, and have an acceptable kidney transplant offer, they will be randomized by the Cedars-Sinai Research Pharmacy to receive study drug vs. placebo. Drug and placebo will be prepared by the Cedars-Sinai Research Pharmacy and conveyed to the operating room in a blinded manner.

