4.2.2 Exclusion Criteria

- 1) Patients with a known pro-thrombotic disorder. (eg. Factor V Leiden)
- 2) Patients with a history of thrombosis or hyper-coagulable state, excluding access clotting.
- 3) Patients with a known hypersensitivity to treatment with C1INH or blood products.
- 4) Patients with an abnormal coagulation function. (INR ≥ 2 , PTT> 50, PLT<80,000) who are not on anti-coagulation.
- 5) Patients with known active presence of malignancies.
- 6) Patients who are positive for Hep B, Hep C, or HIV PCR test.
- 7) All zero mismatch kidneys.
- 8) Recipients of multi-organ transplants. (kidney and any other organ) Recipients of kidney allograft from donors who: < 40 years of age, CIT < 18 hours, serum creatinine ≤ 1mg/dl.
- 9) Recipients of kidney allograft that was on pump preservation for any period prior to transplantation.
- 11) Recipients of kidney allograft from a living donor.
- 12) Female subjects who are pregnant or lactating.

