4.6.3 Assessment Periods

4.6.3.1 Screening Procedure - Day -30 to Day 0

Prior to screening activities, each patient must be given an opportunity to ask questions and to understand the details of study participation. This consent process must be documented in the patient's source documents and evidenced by the patient signing the informed consent form.

After signing the ICF, each patient will be assigned a patient identifier number that will be used on all subject documentation. Numbers will be assigned in ascending sequential order. This number will also correspond to the patient number entered on study materials.

The Principal Investigator or qualified and assigned Subinvestigator will review the inclusion and exclusion criteria and laboratory test data to confirm eligibility of each subject.

The screening procedures will include the following:

- Informed consent
- Medical history
- Inclusion/Exclusion criteria review
- Vital signs/weight
- Complete physical examination (including DVT exam)
- 12-lead ECG (w/in 6 months)
- Chest X-ray (w/in 6 months)
- Hematology & chemistry profile
- PT, PTT, D-Dimer, Fibrinogen
- Review historical serologies for HIV, HBV, HCV, CMV and EBV
- Pregnancy test (for WOCP)
- Urine output measurement
- Urinalysis
- Concomitant medications
- Pneumococcal vaccine & Neisseria menigitides

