4.6.3.2 Day 0 - Day of Transplantation

- Inclusion/Exclusion criteria (pre-transplant)
- Vital signs (pre- and post-transplant)
- Physical examination (pre- and post-transplant)
- Randomization (pre-transplant)
- Hematology & chemistry profile (pre- and post-transplant)
- PT, PTT and INR (pre- and post-transplant)
- Concomitant medications (pre- and post-transplant)
- ECG (pre-transplant)
- Chest x-ray (pre-transplant)

- Serum Creatinine (pre-and post-transplant, within 4-hours of surgery)
- Clinical Assessment (post-transplant)
- Berinert vs. Placebo infusion (on call to OR)
- C1 inhibitor, C3, C4 levels (prior to dose #1 of C1INH or placebo)
- Campath 1H or Thymoglobulin administration

•

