Appendix A

Study visit										
	Screening	Transplant Day 0 (Infusion #1 C1INH vs Placebo)	Day 1±6 hrs (Infusion #2 C1INH vs Placebo)	Day 2±6 hrs	Day 3±6 hrs	Day 4±6 hrs	Day 5±1 days	Day 6±2 days	Day 7±3 days *	Day 14 ±3 days
Informed Consent	Х									
Inclusion/exclusi on criteria review	^ X									
Medical History	X									
Complete Physical Exam (Including DVT Exam) (1)	X	X	X	X	Х	X	X	X	x	
Vital										
signs/weight	Χ	Х	X	Х	Х	Х	Х	Х	Х	Х
12-lead ECG (w/in 6M)	Х									
Chest X-ray (w/in 6M)	Х									
Safety laboratory tests (CBC, CMP)	X	Х	Х	Х	х	Х	Х	Х	Х	Х
PT, PTT, D. Dimer, Fibrinogen	Х	Х	Х						Х	
Review Historical Serologies for HIV, HBV, HCV, CMV and EBV	X									
Pregnancy test (for WOCP)	X									
Urinalysis	Х									Х
Urine Output		v	v	V	V	Х	V	Х		
Measurement Estimated GFR (using MRDR or Cockroft & Gault		X	X	X	X		X		X	
equation)			Х	Х	Х	Х	Χ	Х	Х	Χ

OOMITEDENTIA		OTTIVII (DCI	ernerco, in	1 Deady	±11 1(±0	11101 11	amopia			
Allograft biopsy		Х								
Dialysis	1		+	+						
Assessment	ı	X	X	Х	Х	Х	Х	Χ	х	Х
Assessment for					1					
DVT (Using Wells	ı									
Criteria Score)	ı									
(2)		X	Х						Х	
Pneumococcal	ı									
Vaccine &	ı									
Neiserria	ı									
Menigitides	Х				 				 	 
Berinert® vs	ı									
Placebo Infusion	ı									
_		X	Х		 	 	 	  '	 	1
C3, C4 Levels		Χ	Х		 	 		'	Х	
C1 Inhibitor				T						
Level (Prior to	1									
each infusion)		Χ	X						Х	
Campath or	1									
Thymoglobulin	ı									
administration	 	X			 		 		 	
Concomitant	ı									
medications	Х	X	Х	Х	X	Х	Х	Χ	Х	Х
Adverse Event	ı									
Monitoring	ı		X	Х	X	Х	Х	Х	Х	Х
Acute Rejection										
Assessment	1									

- (1) DVT exam will be done on day 0 and day1 (days Berinert vs.Placebo are given)
- (2) For scores indicating high risk for DVT, patient will have Doppler ultrasound.

*Day 4-7 assessments should be performed daily until the patient is discharged.

**If patient is discharged prior to day 7, day 7 lab assessments should be performed.

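### The only scheduled pregnancy test falls in the 30-day screening window and none accompanies the Day 0 eligibility review, so an undetected pregnancy would pass every scheduled check

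*Combined protocol and SAP*

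**What the plan says.** The eligibility rule in section 4.2.1, item 7, has two parts. The first is the test: "Women of childbearing potential must have a negative pregnancy test prior to randomization". The second is that these women use acceptable birth control. The synopsis (section 2.2) repeats the rule. Neither place limits how old the negative result may be. Section 4.2.2, item 12, excludes "Female subjects who are pregnant or lactating" and names no test or time.

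The test appears in one visit list, section 4.6.3.1, headed "Screening Procedure - Day -30 to Day 0". Appendix A gives it one mark, under Screening.

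Section 4.6.3.2 (Day 0) lists a pre-transplant review of the eligibility criteria, randomisation and the first infusion. It also lists pre-transplant vital signs, physical examination, hematology and chemistry, PT, PTT and INR, ECG and chest X-ray. It lists no pregnancy test.

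On sequence, section 4 (Investigational Plan) says: "Once eligible patients are identified, consented, and have an acceptable kidney transplant offer, they will be randomized". Under section 4.5.8, study staff tell the pharmacist that a patient is eligible, and the pharmacist then prepares the blinded treatment.

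**The concern.** An exclusion works only as well as the information available when it is applied. Pregnancy status can change within 30 days, and randomisation waits for a deceased-donor kidney, whose date the study does not control. Because a test at any point in the screening window satisfies item 7, the Day 0 review may have to apply the pregnancy exclusion on an old result, with nothing scheduled to update it.

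What is at stake is patient safety, not inference. A woman with an unrecognised pregnancy could receive the study infusions. The protocol treats pregnancy as important: it excludes for it, tests for it, and in section 7.3 requires any pregnancy during the study to be reported on the same timelines as a serious adverse event, with follow-up of the outcome.

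**Working it through.** The protocol gives no figure to reproduce. The check sets the sections side by side and works out the permitted age of the test.

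| Place | Pregnancy provision | Timing |
|---|---|---|
| 4.2.1, item 7 (and synopsis) | Negative test, plus birth control | Before randomisation; no maximum age |
| 4.2.2, item 12 | Pregnant or lactating women excluded | No test or time named |
| 4.6.3.1 Screening | Test listed | Day -30 to Day 0 |
| 4.6.3.2 Day 0 | No test listed | Eligibility review, randomisation and first infusion listed |
| 4.6.3.3 to 4.6.3.5, later visits | No test listed | Day 1 to Day 90 |
| 4.6.4.9 Laboratory profile | No pregnancy marker among the named measurements | Drawn on Day 0 before and after transplant |
| Appendix A | One mark | Screening column |

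**Age of the result at Day 0.** Age = day of randomisation minus day of test.
- Earliest permitted test: 0 - (-30) = 30 days.
- Latest permitted test: 0 - 0 = 0 days.

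The permitted range is therefore 0 to 30 days. Nothing in the documents says where in that range a typical patient falls.

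**Could another Day 0 item supply the information?** The blood profile in section 4.6.4.9 does not name a pregnancy marker, and no other listed item is a pregnancy test. The Day 0 review of criteria would stop a woman known to be pregnant, but would not itself reveal a pregnancy nobody knows about.

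**Comparison with another exclusion.** Item 4 of section 4.2.2 uses INR, PTT and platelet limits. PT, PTT and INR are repeated before transplant on Day 0, and so is the hematology profile, which includes platelets. The protocol thus refreshes the laboratory values behind that exclusion on the day and does not do so for pregnancy.

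**Reliability of the table.** Appendix A was damaged when the text was extracted, so its marks should not be relied on alone. The single Screening mark agrees with the separate lists in sections 4.6.3.1 and 4.6.3.2.

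**The case against.** The strongest reply is that the protocol already covers the interval. Item 7 requires birth control as well as a test, item 12 turns on being pregnant rather than on a test result, and the criteria are reviewed again on Day 0. The screening window includes Day 0, so a site may test that day. Much of eligibility (ABO match, donor category, cold ischemia time, pump use) cannot be settled before a kidney is offered, so late screening is plausible. The documents also set no standard that a test within 30 days would breach.

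Much of this stands, and it rules out several stronger readings that a reader might infer:

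- *That a pregnant woman meets every written criterion.* She does not; she fails item 12. The gap concerns a pregnancy that is not known.
- *That the sections contradict one another.* They do not. A screening test does precede randomisation. What is missing is a limit on its age or a test tied to the Day 0 review.
- *That the gap is usually days or weeks.* Section 4 gives the order of events but no interval.
- *That enrolment causes the exposure to immunosuppression.* A transplant recipient needs it whether or not she enrols, and maintenance follows institutional guidelines (section 4.5.5.2). The protocol does restrict the induction agent (section 4.5.5.1), but the exposure that enrolment adds is mainly the study infusions.
- *That a Day 0 test would close the gap completely.* A very early conception would still be missed.

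What the reply does not remove is that a Day -30 result complies fully and that nothing requires a later one. The protocol did not treat birth control alone as sufficient, since item 7 asks for both.

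**Conclusion.** The point holds as a minor safety gap in the schedule. A pregnancy undetected at screening, or begun since despite the birth control requirement, would pass every scheduled check up to the first infusion. The qualifying test may be up to 30 days old.

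The number of women affected cannot be calculated, because the documents do not give the share of women of childbearing potential among the 70 planned patients, the usual interval from screening to transplant, or a rate of contraceptive failure. It is probably very small: the trial enrols dialysis patients of both sexes aged 18 to 70, with birth control required. The documents give no fetal-risk data for C1INH, so the harm per case cannot be sized from them either. No endpoint, analysis or power figure is affected.

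The conclusion assumes that the visit lists are complete as written and that no site procedure outside the protocol adds a Day 0 test.

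**What to change.** Reconcile section 4.2.1 (item 7), section 4.2.2 (item 12), sections 4.6.3.1 and 4.6.3.2, and Appendix A, so that the timing of the scheduled pregnancy test matches the Day 0 pre-transplant eligibility review it informs. State that the result must be available before the pharmacy is told of eligibility under section 4.5.8. Whether a screening test is also kept is for the sponsor and investigator to decide and record.

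The cost is wording in the two visit lists and the corresponding Appendix A entry. Blood is already drawn before transplant on Day 0, so no new visit is needed. There are two downsides. The result has to be back before randomisation, when time is short. And if the screening test were dropped rather than kept, a pregnancy would first be found only after an organ had been offered.

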4.2.2 Exclusion Criteria

- 1) Patients with a known pro-thrombotic disorder. (eg. Factor V Leiden)
- 2) Patients with a history of thrombosis or hyper-coagulable state, excluding access clotting.
- 3) Patients with a known hypersensitivity to treatment with C1INH or blood products.
- 4) Patients with an abnormal coagulation function. (INR ≥ 2 , PTT> 50, PLT<80,000) who are not on anti-coagulation.
- 5) Patients with known active presence of malignancies.
- 6) Patients who are positive for Hep B, Hep C, or HIV PCR test.
- 7) All zero mismatch kidneys.
- 8) Recipients of multi-organ transplants. (kidney and any other organ) Recipients of kidney allograft from donors who: < 40 years of age, CIT < 18 hours, serum creatinine ≤ 1mg/dl.
- 9) Recipients of kidney allograft that was on pump preservation for any period prior to transplantation.
- 11) Recipients of kidney allograft from a living donor.
- 12) Female subjects who are pregnant or lactating.

4.3 Removal Of Subjects From Study

A subject who is withdrawn is one who discontinued in the clinical study for any reason.

Subjects may be withdrawn from the study for the following reasons:

- At their own request or at the request of their legally acceptable representative.
- If, in the investigator's opinion, continuation in the study would be detrimental to the subject's well being.
- At the specific request of the sponsor.

In all cases, the reason for withdrawal must be recorded in the case report form and in the subject's medical records.

Patients have the right to withdraw from the study at any time for any reason without penalty or prejudice. The Investigator also has the right to withdraw patients from the study if he/she feels it is in the best interest of the patient or if the patient is uncooperative or non-compliant. It is understood by all concerned that an excessive rate of withdrawals can render the study un-interpretable; therefore, unnecessary withdrawal of patients should be avoided. Should a patient decide to withdraw, all efforts will be made to complete and report the observations, and early withdrawal procedures, as thoroughly as possible.

The Investigator should contact the patient either by telephone or through a personal visit to determine as completely as possible the reason for the withdrawal. A complete final evaluation at the time of the patients withdrawal should be made with an explanation of why the patient is withdrawing from the study. If the reason for removal of a patient from the study is an adverse event or an abnormal laboratory test result, the principal specific event or test will be recorded on the CRF. For all patients who are withdrawn pre-maturely, every attempt should be made to assess the patient's status (i.e. patient and graft survival, malignancies, etc.) at 30 days after administration of the last dose of study medication.

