4.5.4 Selection Of Doses In The Study

4.5.4.1 Berinert® (C1INH Dosing)

For the planned study, subjects will receive C1NH 50U/kg (round to the nearest 500units) (maximum dose: 4000U) pre-operatively over a period of 10-20 minutes at any one point in time, from time of induction of anesthesia up to the beginning of renal vein anastomosis before graft reperfusion. For all dose reconstitution, Berinert® is provided in single dose vials of 500 units. Each vial will be reconstituted in 10 ml sterile water for injection). Placebo will be administered in an identical volume. An additional dose of Berinert® (50U/kg,actual body weight, maximum dose 4000U) vs. placebo will be administered at 24 hours post-surgery.

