4.5.7 Selection And Timing Of Dose For Each Subject

The active treatment arm (Berinert® 50U/kg, maximum dose 4000U) will be compared to a placebo control treatment arm, with a total of 35 adult subjects in each study group. A total of 70 adult subjects will be enrolled in the study and additional subjects will not be enrolled to replace dropouts. This design is statistically powered to show differences in DGF with a 30-50% reduction in DGF predicted for the Berinert® study group. Treatment effect will be investigated following intravenous treatment with two doses of Berinert® or an equivalent volume of placebo (0.9% normal saline) pre-operatively prior to graft reperfusion and repeated 24 hours post-transplantation.

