4.6.1.2 Secondary Efficacy Endpoints

- Daily serum creatinine for seven days post transplant or until discharge.
- Daily Calculated Creatinine Clearance for seven days post transplant or until discharge.
- Serum creatinine at 14, 28, 60, and 90 days post transplant.
- Total urine output in hours 16-24, 40-48 post transplant.
- Rate of dialysis use at 14, 28, 60, and 90 days post transplant.
- Dialysis duration at 14, 28, 60, and 90 days post transplant.
- Calculated creatinine clearance at 14, 28, 60, and 90 days post transplant.

CONFIDENTIAL

- Rate of acute cellular and antibody mediated rejection episodes by day 90.
- Patient and graft survival by day 90.
 - Protocol renal transplant biopsy at time of implantation.
 - Incidence of DGF as categorized by a DGF scale of increasing severity as follows:

Grade 1 - immediate urine production and no need for dialysis with creatinine reduction ratio (CRR) between time 0 of transplantation and day 7 post-transplantation >70%

Grade 2 - creatinine reduction ratio (CRR) between time 0 of transplantation and day 7 post-transplantation of >70% with need for dialysis

Grade 3 - creatinine reduction ratio (CRR) between time 0 of transplantation and day 7 post-transplantation <70% with no need for dialysis

Grade 4 - creatinine reduction ratio (CRR) between time 0 of transplantation and day 7 post-transplantation of <70% with need for dialysis

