4.6.2.1 Secondary Safety Endpoints

- Chemistry and coagulation parameters
- Patient survival at day 90.
- Graft survival at day 90.
- Rate of acute cellular and antibody mediated rejection episodes at day 90.

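### Section 4.3 sets no day 90 follow-up for withdrawn patients: its only dated check falls at about day 31, up to 59 days before the survival, graft and rejection endpoints

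*Combined protocol and SAP*

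**What the plan says.** Section 4.3 (Removal Of Subjects From Study) sets three duties for a patient who leaves early.

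- At withdrawal: "A complete final evaluation at the time of the patients withdrawal should be made".
- Where the patient decides to leave: "all efforts will be made to complete and report the observations, and early withdrawal procedures, as thoroughly as possible". No visit or day is named.
- For all premature withdrawals: an attempt to learn how the patient and graft are faring, due "at 30 days after administration of the last dose of study medication". The items named are patient survival, graft survival and malignancies.

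Section 4.5.4.1 times the second and final dose: active drug or "placebo will be administered at 24 hours post-surgery".

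The outcomes at issue are set later. The Secondary Safety Endpoints include "Graft survival at day 90", with patient survival and cellular and antibody-mediated rejection at the same time point. Section 4.6.1.2 lists "Patient and graft survival by day 90" among the secondary efficacy endpoints, along with dialysis use and duration at days 14, 28, 60 and 90. Section 4.6.3.5 places the rejection assessment at the day 90 visit (±5 days) and adverse event assessment at the day 60 and day 90 visits.

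Section 4.5.7 plans 35 patients per arm and says that "additional subjects will not be enrolled to replace dropouts". The synopsis describes the analysis only as descriptive and comparative, and Section 6.1 has a heading with no text under it. I found no expected withdrawal rate, analysis set or rule for missing outcomes.

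**The concern.** The dated check is tied to the last dose, while the endpoints are tied to the transplant. Because dosing ends on day 1, the two clocks finish about two months apart. A site that does exactly what Section 4.3 dates will have met its obligation and may still not know whether a withdrawn patient was alive, had a functioning graft or had been treated for rejection at day 90. The check also names patient survival, graft survival and malignancies, and leaves rejection and dialysis to an open-ended 'etc.'.

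Withdrawal may not be independent of outcome. Section 4.3 lets the investigator remove a patient whose well-being would suffer from continuing, and it foresees removals for an adverse event or an abnormal laboratory result. If such removals differ between arms, a comparison among patients with known day 90 status can be distorted.

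Safety is the primary objective (Section 2.1). The day 90 survival, graft survival and rejection items are secondary safety endpoints. The Primary Safety Endpoints paragraph, however, covers adverse events including death and thrombosis, so late events of those kinds could also go unrecorded in withdrawn patients.

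**Working it through.** The plan gives no figure for this point to reproduce, so the check is calendar arithmetic followed by bounds on a proportion.

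**Inputs**

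- Last dose: about day 1 (Section 4.5.4.1).
- Dated check: 30 days after the last dose (Section 4.3).
- Endpoint: day 90; visit window ±5 days (Section 4.6.3.5).
- Patients per arm: 35 (Section 4.5.7).
- Withdrawals with unknown day 90 status: not stated. I assume *w* = 1, 2 or 3 in an arm.

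**Timing**

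- Check day = 1 + 30 = day 31 (day 30 if only the first dose was given).
- Gap to nominal day 90 = 90 − 31 = 59 days, or 59/90 = 65.6% of the follow-up period.
- With the visit window: 85 − 31 = 54 days to 95 − 31 = 64 days.

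**Who has which gap**

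- Withdrawal by about day 31: the last dated contact is day 31, so the gap is 59 days.
- Withdrawal on a later day *d*: the 30-day check has already passed and the last required contact is the final evaluation on day *d*, so the gap is 90 − *d*. For *d* = 75 that is 15 days.
- Death, graft loss or rejection recorded before last contact: that outcome by day 90 is already settled. Only new events after last contact are unknown.

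**Effect on an arm's day 90 rate**

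With *x* known events and *w* unknown patients among 35, the rate lies between *x*/35 and (*x* + *w*)/35, a width of *w*/35.

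| *w* unknown | Width *w*/35 | Range if *x* = 2 known graft losses (illustration) |
|---|---|---|
| 1 | 2.9 points | 2/35 = 5.7% to 3/35 = 8.6% |
| 2 | 5.7 points | 5.7% to 4/35 = 11.4% |
| 3 | 8.6 points | 5.7% to 5/35 = 14.3% |

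If *w* patients are unknown in each arm, the between-arm difference can move by up to *w*/35 in either direction, so ±8.6 points for *w* = 3. The *x* = 2 column is an assumption, chosen to show that when events are few the unknown patients can outnumber the known events.

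**What is not affected**

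The primary efficacy endpoints in Section 4.6.1.1 all fall within 7 days of transplant. The 30-day rule does not bear on them, nor on dialysis at days 14 and 28, which precede the check.

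**The case against.** The other side has a good deal to say.

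First, a reader might infer that withdrawn patients are seen only at the 30-day check. Section 4.3 does not say that. It requires a full evaluation at withdrawal and best efforts to complete the observations, and the 30-day check is worded as a required attempt, not as a limit. This stands. The best-efforts sentence could be read as reaching later visits, but it names no day, is written for patients who choose to leave, and is followed by a specific rule that a site could reasonably take as sufficient. It narrows the gap without closing it.

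Second, a reader might infer that day 90 outcomes will be missing for every withdrawn patient. That is too strong. Events before last contact are known, and Section 7.3 requires each serious adverse event to be followed until it resolves or stabilises, so an event already under way is not dropped.

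Third, 59 days is a maximum for the usual two-dose patient, and later withdrawals lose less.

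Fourth, withdrawals may be few. Both doses are over by 24 hours after transplant, what remains is largely observation, and Section 4.3 discourages unnecessary withdrawal. The documents establish neither the number nor the direction of any bias. This also stands, and it limits how large the problem can be said to be.

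**Conclusion.** The gap is real: no part of the protocol expressly asks for day 90 status after withdrawal, and the one dated check falls up to 59 days before the endpoints it would need to inform. New deaths, graft losses, rejections and serious events after last contact may be missed in withdrawn patients.

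The size rests on an assumption, because no withdrawal rate is given. With 1 to 3 unknown patients in an arm of 35, that arm's day 90 rate is uncertain by 2.9 to 8.6 points. These are worst-case bounds, not estimates of bias.

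It would be tempting to conclude that the primary safety comparison will be biased. The documents support only that it could be: withdrawal related to outcome is plausible from the permitted reasons but is not shown, and the outcomes most directly exposed are secondary. The point deserves correction because the remedy is cheap and unreplaced dropouts in a 70-patient trial leave little slack.

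**What to change.** In Section 4.3, keep the 30-day check and add a check at day 90 (±5 days), by telephone or chart review, for every withdrawn patient unless consent for follow-up is itself withdrawn. Record vital status, graft status, dialysis, rejection and serious adverse events, with dates. Have the case report form distinguish leaving study visits from refusing further follow-up.

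In Section 6.1, state that all randomised patients are analysed in their assigned arm. For survival, graft survival and rejection, censor patients whose day 90 status remains unknown at last contact. Censoring assumes that those lost resemble those followed, so add a best/worst-case sensitivity analysis of the kind shown above. Day 90 dialysis is a status at one time point, so use the same bounds for it directly.

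The cost is one extra contact or record review per withdrawn patient and a short paragraph of analysis text. The sample size does not change. Section 4.3 already uses telephone contact to establish the reason for withdrawal, so no new procedure is needed.
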